### 7.5.2 Definition of a Completed Patient

A **subject** is considered complete when s/he meets **either** of the following criteria:

- received all scheduled doses of DAR-901 and completes the study visit at 24 months, **or**
- received at least one dose of DAR-901 **and** had treatment discontinued due to a DLT event.

## 7.6 Procedures for Managing the Study

### 7.6.1 Discontinuing Study Treatment in Individual Patients

Study treatment may be discontinued in an individual patient for **any** of the following reasons:

- The subject withdraws from study participation by their own decision (“withdrawal of consent”); this may happen at any time and for any reason without prejudice for their continued care.
- The subject has a DLT event as defined in Section 7.5.1.
- The Investigator determines, based on their judgment, that discontinuation of study treatment is in the subject’s best interest, e.g., due to an adverse event, noncompliance, or any reason, whether or not related to study drug or study procedures.

If study treatment is discontinued prematurely, the reasons will be recorded and, if possible, the EOS visit will be performed as specified (see Section 11). If a subject cannot be seen, attempts will be made to contact the subject by telephone.

### **7.6.2 *Replacement of Subjects***

A subject who is not IGRA negative at 2 months (Visit 2) or who is lost to follow-up before Visit 2 will not be part of the efficacy cohort and will be replaced to ensure the requirements for achieving the target sample size are met. A replacement subject will be identified by a distinctive subject number and will receive the same treatment as the subject being replaced.

### **7.7 Data and Safety Monitoring Board (DSMB)**

As part of the comprehensive risk management program, the Sponsor will establish a 3 person Data and Safety Monitoring Board (DSMB) comprising two independent physicians with clinical trials experience (preferably including early phase and/or vaccine studies) and a representative of the Sponsor who has prior experience with SRL-172. One member will be from Tanzania.

The DSMB will serve the following functions:

- Review the Protocol and suggest possible changes prior to study initiation.
- Be notified of and review promptly any Serious Adverse Events. If the DSMB considers that the SAE may be treatment-related, they may request to be unblinded in order to proceed to a recommendation regarding the ongoing conduct of the Study.
- Recommendations regarding the conduct of the study may include, but are not limited to, increasing safety monitoring procedures or tests; terminating study treatment.
- Review blinded safety and efficacy data every 6 months
- Recommendations to the sponsor will be based on a majority vote.

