### ***2.8.5 Determination of Sample Size***

The sample size of 650 subjects (325 in each treatment group) is based on an expected 7% annual IGRA conversion rate among placebo recipients who remain IGRA-negative at 2 months (pre-dose 2; IGRA conversions before dose 2 may represent TB infection acquired prior to the dose 1). The sample size is calculated with 80% power to detect vaccine efficacy of 50% in preventing TB infection. Loss to follow-up is estimated at 5-10% per year. A blinded interim analysis will be conducted after results of the 14 month IGRA are available on 200 subjects. The study duration and number of repeat IGRAs will be increased if needed to detect sufficient endpoints.

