#### 12.1.3 *Serious Adverse Event (SAE)*

An AE is **serious** when the subject outcome is one or more of the following:

- Death.
- Life-threatening, meaning that the subject was at immediate risk of death from the event at the time that the event occurred. It does not include an event which hypothetically might have caused death if it occurred in a more severe form.
- Hospitalization, initial or prolonged, meaning that a hospital admission and/or prolongation of a hospital stay was required for the treatment of the AE, or occurred as a consequence of the event. It does not include a pre-planned elective hospital admission for treatment or diagnostic procedures, or, in general, a hospital admission of less than 24 hours duration.
- Disability or incapacity that is persistent or significant.
- Congenital anomaly or birth defect.
- Important medical event that, although not immediately life-threatening, requires intervention in order to prevent one of the other serious outcomes listed above. Examples of such events are allergic bronchospasm requiring intensive treatment in an emergency room or at home; blood dyscrasias or convulsions that do not result in hospitalization; or the development of drug dependency or drug abuse. For the present study a new case of active tuberculosis will be considered an SAE in this category.

 A medical product may be a drug or a device being used either prior to or after regulatory approval. The medical product in this protocol will hereafter be referred to as study drug (synonym: investigational agent).

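### Section 7.7 gives a Sponsor representative a vote on the three-person DSMB with no bar on unblinded SAE allocations, while the scheduled safety reviews carry no arm information

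*Protocol*

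**What the plan says.** On composition, section 7.7 states that "the Sponsor will establish a 3 person Data and Safety Monitoring Board (DSMB) comprising two independent physicians with clinical trials experience", and adds as third member "a representative of the Sponsor who has prior experience with SRL-172". On decisions, it says that "Recommendations to the sponsor will be based on a majority vote". It does not describe the Sponsor member as non-voting, limit that member to open sessions, or require recusal when allocations are discussed.

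On access to arm data, section 7.7 provides one route: "If the DSMB considers that the SAE may be treatment-related, they may request to be unblinded in order to proceed to a recommendation". The pronoun covers the whole board. Section 9.9.1 also has the DSMB give prior approval before the investigator unblinds an individual subject, emergencies excepted.

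On scheduled work, section 7.7 tells the board to "Review blinded safety and efficacy data every 6 months". The one-year endpoint analysis in section 2.4.2 and the interim analysis in section 2.8.5 are also described as blinded. The protocol schedules no by-arm safety review.

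Two further provisions bear on the point. Section 12.1.3 says "For the present study a new case of active tuberculosis will be considered an SAE in this category", while section 2.8.3 makes active TB an exploratory efficacy endpoint. Section 2.8.5 says "The study duration and number of repeat IGRAs will be increased if needed to detect sufficient endpoints".

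**The concern.** The arrangement has two weaknesses.

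The first is independence. A DSMB advises the Sponsor from outside the Sponsor. Here the Sponsor has a vote on advice addressed to itself, including advice to terminate study treatment, and its representative may be present when treatment assignments are disclosed.

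The second is sight of harm. The subjects are healthy 13- to 15-year-olds receiving an investigational vaccine. Arm information reaches the board only one case at a time, and only when that case already looks treatment-related. A pattern of ordinary-looking events that is notable only because it sits in one arm would not trigger that route. The scheduled reviews, which should catch such a pattern, are blinded.

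**Working it through.** **Voting.** Three members, majority rule, so two votes carry a recommendation.

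| Independent physicians | Outcome |
|---|---|
| Both in favour | Carried whatever the Sponsor member votes |
| Both against | Rejected whatever the Sponsor member votes |
| Split 1:1 | Decided by the Sponsor member |

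The Sponsor member can never carry a vote alone, but settles every split between the physicians.

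**Who sees allocations.** The unblinding clause requires three steps: an SAE is notified, the board considers that it may be treatment-related, and the board asks to be unblinded. Nothing in sections 7.7, 9.9 or 9.9.1 withholds the answer from the Sponsor member. Because active TB is an SAE, each case is notified to the board, but its arm is disclosed only if the second and third steps follow.

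**What a blinded review can show.** Section 7.7 contrasts its blinded review with a request to be unblinded, so the plain reading is that the review carries no arm information. The protocol gives no event count, so assume 12 pooled events. Allocation is 1:1 (section 2.4), so with no vaccine effect the number in one arm is Binomial(12, 0.5). For a larger share k above 6, the two-sided p-value is 2 × Σ C(12, j) / 2^12, summed over j = k to 12; for 6:6 it is capped at 1.

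| Split | Calculation | p | Blinded report |
|---|---|---|---|
| 6:6 | capped | 1.00 | 12 events |
| 9:3 | 2 × 299/4096 | 0.146 | 12 events |
| 10:2 | 2 × 79/4096 | 0.039 | 12 events |
| 11:1 | 2 × 13/4096 | 0.006 | 12 events |

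The four cases are indistinguishable in a pooled report.

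**What a by-arm table could add.** The protocol states no SAE rates, so these are assumptions. The last column is the exact probability that a two-sided Fisher test gives p < 0.05 with 325 per arm, in one look at all 650 subjects.

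| Assumed rate, placebo vs vaccine | Expected events | Flagged by arm |
|---|---|---|
| 1% vs 4% | 3.25 vs 13 | 63% |
| 2% vs 5% | 6.5 vs 16.25 | 48% |
| 1% vs 3% | 3.25 vs 9.75 | 34% |
| 0.3% vs 1% | 0.975 vs 3.25 | 5% |

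A formal test on a by-arm table is useful for moderate excesses and of little use for very rare events. In the first row a pooled report would show about 16 events in 650 (2.5%) with no comparator. An early review with fewer subjects would detect less than the table suggests.

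**The case against.** **The board is not without information.** It is notified of every SAE and may ask to be unblinded, receives SUSARs within 7 or 15 days (section 12.4.3), and can recommend terminating treatment. Section 7.5.1 allows unblinding to settle whether a dose-limiting event occurred on DAR-901. Table 2 places immunization in months 0 to 8, so about one six-monthly review falls while dosing continues. This stands as a limit on the size of the concern. These routes nevertheless start from single events, and none compares the arms.

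**The word blinded is undefined, and a charter is not shown.** Blinded could mean tables by masked arm. The revision history mentions a DSMB charter, which may contain closed-session or recusal rules. Both are possible. But section 7.7 itself fixes composition, voting and review content, and states no such restriction. A charter that said otherwise would conflict with it.

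**The Sponsor's vote has limited force.** The independents outvote the Sponsor member when they agree, and the Sponsor may terminate the study at any time under section 7.8. That is correct. The vote matters only in a split, which is also when independence matters most.

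**A stronger reading is tempting and fails.** A reader might infer that, because active TB is an SAE, the Sponsor gains arm-level efficacy knowledge that could steer the extension of follow-up or unblind the interim look. The text does not support this. Unblinding is conditional and on request. A TB case after a heat-inactivated vaccine with no living organisms (section 12.5) would not readily be judged treatment-related. Active TB is expected to be very low and is exploratory. IGRA conversion, the primary endpoint, is not listed as an SAE, so its split by arm is not exposed this way. The trigger for extension is whether there are sufficient endpoints, read from a blinded analysis.

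**Conclusion.** The concern holds as a point of governance and safety oversight. It does not affect sample size, type I error or the primary analysis.

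Two findings follow from section 7.7. The Sponsor's representative has one of three votes, decisive when the independent physicians disagree, and is not excluded from allocations disclosed on a suspected SAE. On the plain reading of blinded, the scheduled reviews cannot reveal an excess of events in one arm.

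The size of the second finding depends on event rates that the protocol does not give. Under the assumed rates above, a single by-arm look at full enrolment would flag an excess in about 5% to 63% of trials. Phase 1 reported no SAEs (section 5.4.1), so for SAEs alone the lower part of that range may be more relevant. The structural point, that a pooled count hides its split, needs no assumed rate.

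The leak of efficacy information through active TB is possible but small. The change is worth making because it is cheap and removes both weaknesses.

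**What to change.** Amend section 7.7, and align the charter with it, as follows.

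1. Make the Sponsor representative a non-voting adviser who attends open sessions only and has no access to individual allocations or by-arm data, including those disclosed when the board asks to be unblinded on an SAE.
2. Leave recommendations to the two independent physicians, and forward a safety concern raised by either one as a recommendation. Requiring both to agree would let one physician block a safety recommendation. Alternatively, fill the third seat with an independent member and keep the majority vote.
3. At each six-monthly review, give the independent members in closed session a table of SAEs, systemic adverse events and CBC abnormalities by coded arm, with decoding on request.
4. Keep injection-site reactions out of the coded tables, or state that including them may reveal the arm. Table 4 in section 5.4.1 reports measurable erythema and induration after DAR-901, so the code could be broken.
5. Keep efficacy data pooled.

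The cost is the Sponsor's vote, one additional table per review, and the risk that the independent members become partly unblinded. Participant procedures, endpoints and sample size do not change.

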### **7.8 Discontinuation of the Study**

The Sponsor may terminate the study at any time for any reason. Subjects would still be followed for safety. In the event the study is terminated, the IECs and appropriate regulatory authorities will be notified of the decision.

## 8. SUBJECT SELECTION

### 8.1 Source of Subjects and Recruitment Methods

Following appropriate Human Studies review and approval, the Investigator may initiate and manage subject recruitment. This will include contact with the Ministries responsible for Education and Health in Tanzania and administrative leaders of secondary schools in Dar es Salaam. To reach an economically and socially diverse population, the study may be announced in newspapers, on the radio, at school functions and on relevant Internet websites.

### 8.2 Subject Disclosures and Restrictions during the Conduct of the Study

This is a Phase 2 study of healthy adolescents. In the interest of their safety and to facilitate accurate assessment of the data, the subjects will agree to the disclosures and restrictions detailed in Table 8-1 for the duration of their participation in the study, i.e., screening visit to End-of-Study (EOS) visit.

**Table 8-1. Subject disclosures and restrictions during the conduct of the study**

Item / Activity	Action	Comment
Prescription medication	Disclosure	Prescription medications in use at the time of screening will be reviewed in detail. Medications subsequently prescribed by physicians other than the Investigator will be disclosed promptly.
Over-the-counter medication	Disclosure	Over-the-counter medications in use at the time of screening will be reviewed in detail. Over-the-counter medications subsequently initiated by the subject will be disclosed promptly.
High-dose Vitamins b	Prohibited	Vitamins and minerals in doses substantially exceeding recommended daily requirements.
Blood donation	Prohibited	Prohibited until 2 months after Dose 3 (usually 6 months after enrollment)

a. Patients will be instructed about the range of products containing St. John's Wort, other herbals, caffeine or xanthines (including chocolate).

b. Vitamins and minerals in doses substantially exceeding recommended daily requirements.

### 8.3 Definitions

#### 8.3.1 *Non-childbearing potential*

Non-childbearing potential is defined as meets **one** of the following two criteria:

- documented hysterectomy or bilateral oophorectomy.

#### 8.3.2 *Effective birth control (contraception) methods*

Effective birth control (contraception) methods means strict abstinence or use of **two** of the following methods: hormonal contraceptive (oral, injectable, implanted [e.g., ImplanonTM], or intravaginal ring), condom, diaphragm, spermicide, or an intra-uterine device.

### 8.4 Subject Selection Criteria

Subject selection criteria are detailed in Section 2.4, including

- Inclusion and Exclusion Criteria (Sections 2.5.1 and 2.5.2, respectively)

#### 8.4.1 *Observed Variances*

Subjects meeting inclusion and exclusion criteria at screening may be scheduled for enrollment. If on Day 0 prior to the first dose, clinical variances are noted compared to screening enrollment may proceed with the approval of the Medical Monitor.

## 9. STUDY TREATMENTS

### 9.1 Study Treatments to be Administered

**Table 9-1. Study treatments**

Role in Study	Identity of treatment	Comments
Investigational	DAR-901	Administered by ID injection
Placebo Control	Sterile Saline for Injection	Administered by the same route and in the same dose volume.

### 9.2 Identity of the Investigational Product

**Table 9-2. Physical and Chemical Properties of Active Ingredient (Drug Substance)**

Name	DAR-901
Vaccine Class	whole-cell, heat-killed organisms
Appearance	Slightly turbid yellow suspension

**Table 9-3. Formulation of DAR-901 for Injection (Drug Product)**

Name	DAR-901 for Injection
Active ingredient	DAR-901
Excipients	Borate-buffered 0.9% NaCl
How supplied	Sterile 2 mL vial containing $0.35 \pm 0.05$ mL of 10 mg/mL DAR-901
Storage	2-8°C
Preparation and handling	Preparation varies by dose level; see Section 9.3 for details.
Administration	The dose is administered as a single intradermal (ID) injection in the deltoid using a fresh sterile needle (approximately 26g).

### 9.3 Preparation and Handling of DAR-901 for Injection by Dose Level

#### 9.3.1 1 mg DAR-901 for Injection

- Gently agitate the vial to assure an even suspension
- Withdraw 0.1 mL from the vial for administration.

Detailed dose-preparation instructions and flow-sheets will be provided in the Pharmacy Manual.

### 9.4 Reference and Blinding Therapy

Sterile Saline for Injection is used as the placebo control and for blinding.

### 9.5 Administration of Study Treatments

Each dose of DAR-901 or placebo will be administered as a single intradermal (ID) injection. The recommended site for injection is the upper deltoid region of the arm, with sequential doses administered in the opposite arm. In the event this recommendation cannot be accommodated due to injury or other issue, the same arm may be used successively, placing the injection at least 5 cm apart.

#### 9.5.1 Variances in Dose Administration Schedule

The protocol permits variance in dose administration of plus or minus two weeks from the nominal scheduled timepoint. Variances that would exceed plus or minus two weeks should be discussed with the Medical Monitor.

## **9.6 Method of Assigning Patients to Treatment Groups**

Subjects will be assigned by computer-generated randomization. Suitable randomization procedures will be established by the CRO data management and clinical services performing the protocol and approved by the Sponsor. The research pharmacist will be provided a list of treatment assignments.

## **9.7 Selection of Dose Levels in the Study**

See Section 7.2.1.

## **9.8 Selection of Dose Number and Interval**

See Section 7.2.2.

## **9.9 Blinding**

Subjects randomized to placebo regimen will receive an injection of Sterile Saline for Injection at the same dose volume as active treatment. The pharmacist is responsible for maintaining the blind, that is, assuring that treatment allocation is not revealed to other study staff or the patients.

### **9.9.1 Procedures for Unblinding Individual Patients during the Study**

There are no specific treatments for the effects of DAR-901; the Investigator should manage patients symptomatically based on any changes observed. Consequently, it is not expected that the treatment allocation for a particular subject will need to be revealed (i.e., unblinded).

If the Investigator needs to unblind the treatment assignment for a particular subject, prior approval by the DSMB should be obtained and the following information entered into the medical record:

- date and time of the last injection,
- reasons study drug was discontinued,
- name of the Medical Monitor who approved unblinding,
- reasons the subject's treatment allocation was unblinded.

In the event of a true medical emergency in which the Investigator judges that the subject cannot be managed safely without unblinding, the Investigator may obtain the treatment allocation directly from the pharmacist at the site. All steps above will be followed, including contacting the DSMB as soon as possible and not more than 24 hours afterwards.

## **9.10 Prior and Concomitant Therapy**

See Section 8.2. Treatments prohibited prior to enrollment are prohibited for the duration of the study.

## **9.11 Treatment Compliance**

All doses will be administered by a study nurse or physician.

## **9.12 Accountability of Investigational Drug Supplies**

The Investigator at each study site will identify trained and experienced personnel to handle the study drug in accordance with the protocol and appropriate GCP and GMP principles. This includes:

- storing the drug in a secure, limited access facility and under the appropriate conditions;
- dispensing and administering study drug only in accordance with the protocol;
- maintaining drug accountability records;
- at the completion of the study, returning or destroying unused study drug in compliance with the written instructions of the Sponsor.

Detailed procedures for accountability of drug product are provided in the SOPs which include requirements for destroying unused drug according to guidelines of the Tanzanian Food and Drugs Authority.

## 10. STUDY EVALUATIONS

Detailed schedules of evaluations are shown in Table 1.

### 10.1 Medical Evaluation

The Investigator will assess the general health of the potential subject at the Screening visit; any new findings observed at subsequent scheduled and unscheduled visits will be recorded.

### 10.2 Vital Signs

Vital signs include temperature, heart rate (HR), respiratory rate (RR) and blood pressure (BP). Where feasible, vital signs should be measured before blood is drawn and after the patient has been sitting comfortably for ~5 min with the BP cuff in place (preferably on the non-dominant arm). BP and HR measurements may be done manually or by automated recorder. Temperature will be obtained using an electronic (rapid reading) device. Respiratory rate will be determined by observation for at least 30 sec.

### 10.3 Laboratory Studies

The laboratory tests indicated below will be performed by an approved laboratory proposed by the Investigator at each site and approved by the Sponsor. Details of procedures for collecting, processing, storing and shipping the blood samples will be provided in the SOPs.

The Investigator may order additional local laboratory tests consistent with their routine standard of care.

#### 10.3.1 Safety Laboratory Tests

**Table 10-1. Complete blood count (CBC)**

Hematocrit	White blood cell differential (if WBC abnormal and clinically significant)
White blood cell count	- Neutrophils
Platelet count	- Lymphocytes
	- Monocytes
	- Eosinophils
	- Basophils

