### 7.5.1 Definition of a Dose-Limiting Toxicity (DLT) Event

A DLT *systemic clinical event* is defined as a treatment-emergent systemic clinical event that meets **all** of the following criteria:

- is assessed by the investigator as related or possibly related to study drug (see Section 12.3.3);
- is of severity (see Section 12.3.4) Grade 2 or higher;
- is of duration >48 hours.

A DLT *injection site reaction* (ISR) is defined as an event that meets **both** of the following criteria:

- occurs at the injection site;
- is of severity Grade 3 or higher.

A DLT *laboratory event* is defined as a confirmed, treatment-emergent laboratory finding that meets **both** of the following criteria:

- is **not** considered consistent with a concurrent clinical event that is assessed as not related or unlikely related to study drug (e.g., an accidental injury, new ART); **and**
- based on pre-specified toxicity criteria (see Section xx) represents an increase of two Grades or more compared to pre-treatment baseline value.

A subject who experiences a DLT event will not receive further doses of study drug. Unblinding may be performed to determine if a DLT event has occurred in a subject receiving DAR-901.

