## 12.6 Grading of Specific Laboratory Safety Tests for Reporting and Analysis

For specific laboratory safety tests shown in Table 18-1 all abnormal results will be graded using the criteria shown, which are taken from the “FDA Guidance for Industry. Toxicity Grading Scale for Healthy Adult and Adolescent Volunteers Enrolled in Preventive Vaccine Clinical Trials. September 2007.” (13).

The grading will be used both in reporting AEs and in the data presentation and analysis of laboratory results. Specifically, the data listings will indicate the appropriate Grade and treatment-emergent changes in these laboratory tests will be summarized as “shift tables” using these grades (see Section 0). This process will assure that the final study report contains complete and consistent analyses of these laboratory safety results.

Treatment-emergent abnormal laboratory results for analytes not shown in Table 18-1 will be reported as AEs using the procedures and criteria detailed in Section 12.1.5.

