## 18. APPENDICES

**Table 18-1. Criteria for Grading Abnormal Results of Specific Laboratory Safety Tests**

Analyte	AE Term	Units	Grade 1	Grade 2	Grade 3	Grade 4
Hb (decr) (F)	Anemia – if baseline WNL	g/dL	11.0 – 12.0	9.5 – 10.9	8.0 – 9.4	< 8.0
Hb (decr) (F)	Anemia – if baseline <LLN decreased from baseline [any]	g/dL	Any decr – 1.5	1.6 – 2.0	2.1 – 5.0	> 5.0
Hb (decr) (M)	Anemia – if baseline WNL	g/dL	12.5 – 13.5	10.5 – 12.4	8.5 – 10.4	< 8.5
Hb (decr) (M)	Anemia – if baseline <LLN decreased from baseline [any]	g/dL	Any decr – 1.5	1.6 – 2.0	2.1 – 5.0	> 5.0
WBC (incr)	increased	cell/mm 	10,800 – 15,000	15,001 – 20,000	20,001 – 25, 000	> 25,000
WBC (decr)	decreased	cell/mm 	2,500 – 3,500	1,500 – 2,499	1,000 – 1,499	< 1,000
Lymphocytes	decreased	cell/mm 	750 – 1,000	500 – 749	250 – 499	< 250
Neutrophils	decreased	cell/mm 	1,500 – 2,000	1,000 – 1,499	500 – 999	< 500
Eosinophils	increased	cell/mm 	650 – 1500	1501 - 5000	> 5000	Hypereosinophilic
Platelets	decreased	cell/mm 	125,000 – 140,000	100,000 – 124,000	25,000 – 99,000	< 25,000

decr., decreased; Hb, Hemoglobin; WBC, White Blood Cells.

 The laboratory values provided in the tables serve as guidelines and are dependent upon institutional normal parameters. Institutional normal reference ranges should be provided to demonstrate that they are appropriate.

 The clinical signs or symptoms associated with laboratory abnormalities might result in characterization of the laboratory abnormalities as "Potentially Life Threatening" (Grade 4). For example, a low sodium value that falls within a grade 3 parameter (125-129 mE/L) should be recorded as a grade 4 hyponatremia event if the subject had a new seizure associated with the low sodium value.

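### Tables 10-1 and 18-1 disagree: for 4 of the 6 graded blood-count analytes the listed CBC does not routinely supply the value that Section 12.6 promises to grade and tabulate

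*Protocol*

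**What the plan says.** Four places in the protocol bear on this.

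- **Section 10.3.1, Table 10-1.** The CBC consists of haematocrit, white cell count and "Platelet count", plus a "White blood cell differential (if WBC abnormal and clinically significant". Haemoglobin is not listed.
- **Section 18, Table 18-1.** Grades are defined for haemoglobin (in g/dL, by sex and by whether baseline was normal or below the lower limit), WBC up, WBC down, lymphocytes, neutrophils, eosinophils and platelets. The abbreviation line reads "decr., decreased; Hb, Hemoglobin; WBC, White Blood Cells"; haematocrit appears neither there nor in any row.
- **Section 12.6.** For the Table 18-1 tests, "all abnormal results will be graded using the criteria shown", and "treatment-emergent changes in these laboratory tests will be summarized as “shift tables” using these grades". The stated purpose is a complete and consistent analysis in the final report. Anything outside the table takes another route: "Treatment-emergent abnormal laboratory results for analytes not shown in Table 18-1 will be reported as AEs", under Section 12.1.5.
- **Section 7.5.1.** A laboratory DLT is judged "based on pre-specified toxicity criteria (see Section xx") and is met when the finding "represents an increase of two Grades or more compared to pre-treatment baseline value".

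Two further provisions matter. Exclusion criterion 6 (Section 2.5.2) removes anyone with a clinically significant abnormal CBC. Section 10.4.1 allows an abnormal screening CBC to be repeated once.

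**The concern.** A shift table needs a baseline grade and a post-dose grade for the same analyte in the same subject. The protocol fixes the analytes to be graded in one table and the analytes to be measured in another, and the lists do not match. A statistical analysis plan cannot repair this, because it cannot grade values that the protocol does not plan to collect.

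Safety is half of the primary objective (Sections 2.2.1 and 6.1), and Section 14.4 names the CBC among the inputs to the primary safety evaluation. If the protocol is followed as written, the haemoglobin part of the laboratory safety tables has no planned data. The differential part has data only from subjects picked out after dosing by an abnormal WBC, so a comparison of the arms on those rows would rest on a selected subset.

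**Working it through.** The protocol states no figure to reproduce here. The check is to match each row of Table 18-1 to Table 10-1.

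| Analyte in Table 18-1 | Rows | Supplied by Table 10-1? |
|---|---|---|
| Haemoglobin (female, male; baseline normal or below the lower limit) | 4 | Not listed; haematocrit only |
| Lymphocytes | 1 | Only if WBC abnormal and clinically significant |
| Neutrophils | 1 | Only if WBC abnormal and clinically significant |
| Eosinophils | 1 | Only if WBC abnormal and clinically significant |
| WBC (increase, decrease) | 2 | Always |
| Platelets | 1 | Always |

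- **By row:** 4 not listed + 3 conditional + 3 always = 10, so 4 + 3 = 7 of 10 are not routinely supplied.
- **By analyte:** 1 not listed + 3 conditional + 2 always = 6, so 1 + 3 = 4 of 6 are not routinely supplied.

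The analyte count is the fairer measure, since four of the seven rows are haemoglobin alone.

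**Haemoglobin.** The grades are in g/dL, and even the choice of row depends on the baseline haemoglobin. The protocol gives no conversion from haematocrit. As an analyte outside Table 18-1, haematocrit goes to AE reporting under 12.1.5 and not to the graded tables.

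**Baseline differential.** At screening a differential requires a WBC that is abnormal and clinically significant. The same finding meets exclusion criterion 6. Within the planned panel, an enrolled subject could have a pre-treatment differential only if a first screening CBC triggered one and the single permitted repeat was then acceptable. For nearly everyone else the baseline cell of a shift table is empty on these three rows.

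**Post-dose differential.** The trigger can miss what the table grades. By Table 18-1's own cut-offs, a WBC from 3,501 to 10,799 is ungraded. Two illustrations inside that range:

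- WBC 5,000 with neutrophils at 19.98%: 5,000 × 0.1998 = 999, which is Grade 3 (500 to 999).
- WBC 8,000 with eosinophils at 8.125%: 8,000 × 0.08125 = 650, which is Grade 1 (650 to 1,500).

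Unless the WBC itself were judged abnormal and clinically significant, the plan calls for no differential in either case. These examples show that the gap exists. The documents give no basis for saying how often it would arise.

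**With the tables aligned.** If Table 10-1 listed haemoglobin and an unconditional differential, 10 of 10 rows would be supplied.

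**The case against.** The case on the other side has several parts.

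- **Section 12.6 governs only results obtained.** On this reading, grading all abnormal results does not promise to measure every row. Table 18-1 is borrowed from a general toxicity scale, and its footnote still discusses sodium, which this trial does not measure, so unused rows prove little. This is fair for the grading sentence taken alone. It does not cover the commitment to shift tables on these tests, or the stated aim of complete and consistent analyses.
- **A conditional differential in healthy adolescents is a legitimate choice.** It is, and the sponsor may keep it. But 12.6 should then not present the differential rows as routinely graded and tabulated.
- **Other provisions soften the gap.** Haematocrit is measured and can lead to an AE, Section 10.3 lets the investigator order additional tests, and Section 10.4.1 allows repeat CBCs. All true, so it would be wrong to say that such abnormalities could never be found. None of this is systematic collection in both arms.
- **The CBC is a small part of safety.** It is one of five inputs in Section 14.4, and Section 2.8.2 mentions only adverse events and vital signs. This limits the weight of the point but does not remove the contradiction.

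A reader might infer that the laboratory grades, the shift tables and the DLT rule cannot be applied at all. The documents do not support that. WBC increase, WBC decrease and platelets are measured at every CBC, and their grades and shifts can be produced in full. A post-dose differential grade also exists whenever the trigger is met. As for the DLT rule, 7.5.1 never names Table 18-1; its reference is blank, so any claim that the rule fails because of Table 10-1 assumes what the blank contains.

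**Conclusion.** The contradiction is real and should be corrected. For 4 of the 6 graded analytes (7 of 10 rows) the listed CBC does not routinely supply the value. For those rows the grading and shift tables in 12.6 cannot be produced systematically, and post-dose differentials would come only from subjects selected by an abnormal WBC. The two WBC rows and the platelet row stand.

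This assumes that Table 10-1 defines what is recorded. The laboratory may report haemoglobin or a differential anyway, but the protocol neither says so nor plans to collect them. The point concerns the laboratory safety analysis only; sample size, power, alpha and the efficacy endpoints are untouched.

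The blank reference in 7.5.1 is a separate defect. Because a DLT event ends a subject's dosing, what fills it is a clinical decision on which this review takes no position.

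**What to change.** In Table 10-1, list haemoglobin and the absolute differential counts at each scheduled CBC and remove the condition on the differential. The 4 mL CBC sample in Section 10.5 is already drawn, so no extra visit is needed; that this volume suffices is an assumption to confirm with the laboratory. For CBCs already taken, recover these values where the laboratory kept them. The documents do not say whether it did, so recovery may be partial, and baseline values that were not kept cannot be recreated.

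If the sponsor prefers to keep the conditional differential, or if past values cannot be recovered, state in 12.6 which rows of Table 18-1 will not be graded or tabulated.

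The cost is protocol and CRF wording and a few more data fields per CBC: four if only the graded analytes are added (haemoglobin, lymphocytes, neutrophils, eosinophils). The second route costs only the wording, but it gives up those rows of the safety tables.

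Separately, the sponsor must resolve the blank section reference in 7.5.1 and reconcile that rule with Tables 10-1 and 18-1, so that whatever criteria are cited rest on values the trial collects before and after dosing.
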